- Merging lesions:
 - When two or more index lesions merge, the smaller lesion should have 0 mm recorded for the current and all future assessments, and the larger lesion should have the longest diameter of the merged lesion recorded for the current assessment and be followed for future assessments.
- Separating lesions:
 - When an index lesion splits into 2 or more lesions, the largest measurable part of the split lesion should be considered to be the previously recorded index lesion with measurements provided for the current assessment and followed for future assessments. The remaining lesions would be non-index lesions. Any new lesions that result from separating should be documented as non-index lesions that were generated by separating and not truly new lesions.

- Index lesion response
 - Immune-related Complete Response (irCR) – complete disappearance of all index lesions in two consecutive observations at least 4 weeks apart
 - Pathologic lymph nodes must have reduction in short axis to < 10 mm
 - Immune-related Partial Response (irPR) – decrease of 30% or greater in tumor burden compared with baseline in two consecutive observations at least 4 weeks apart
 - Immune-related Stable Disease (irSD) - not meeting the criteria for irCR or irPR, in the absence of immune-related progressive disease
 - Immune-related Progressive Disease (irPD) – at least a 20% increase in tumor burden compared with nadir (at any single time point) in two consecutive observations at least 4 weeks apart
 - When the size of the tumor lesion is considered ‘too small to measure’ (eg, less than 5 mm), a default value of 5 mm should be assigned for index lesions. If this is nadir, irPD will be judged from the tumor burden calculated using the default value.
- Non-Index Lesion Response
 - irCR – complete disappearance of all non-index lesions.
 - Pathologic lymph nodes must have reduction in short axis to < 10 mm
 - irPR and irSD – non-Index lesions are not considered in the definition of irPR or irSD. Measurements of non-index lesions are not required, but they are evaluated at each timepoint as ‘present’, ‘absent’ or ‘unequivocal progression’. If a significant partial response is observed in a non-index lesion, it should be described as a comment.

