 - irPD – increases in number or size of non-index lesion(s) does not constitute progressive disease. New lesions that are measurable up to 5 new lesions per organ and 10 total) are included in the calculation of tumor burden in response assessments
- Overall response
 - irCR – complete disappearance of all lesions (whether measurable or not, and no new lesions)
 - Confirmation by a repeat, consecutive assessment no less than 4 weeks from the date of the first documented response
 - irPR – decrease in tumor burden \geq 30% relative to baseline.
 - Confirmation by a repeat, consecutive assessment no less than 4 weeks after the first documentation
 - irSD – not meeting criteria for irCR or irPR, in the absence of irPD
 - irPD – increase in tumor burden \geq 20% relative to nadir (minimum recorded tumor burden) and at least 5 mm absolute increase compared to nadir.
 - Confirmation by a repeat, consecutive assessment no less than 4 weeks from the date of the first documented assessment.

Response confirmation:

- irCR and irPR:
 - the repeat confirmation scan may be performed any time after 4 weeks from the first suspected radiologic evidence of response and may be delayed until the next scheduled scan to avoid necessary procedures
- irPD:
 - In subjects who have initial evidence of radiological PD by irRECIST (irPD on one scan), it is at the discretion of the PI whether to continue a subject on study treatment until repeat imaging is obtained based on their assessment of clinical stability. Subjects may receive study treatment and tumor assessment should be repeated ≥ 4 weeks later in order to confirm irPD per site assessment.
 - In determining whether or not the tumor burden has increased or decreased per irRECIST, the local site investigator should consider all index as well as any incremental new measureable lesion(s).
 - irPD is confirmed at repeat imaging (irPD on two consecutive scans at least 4 weeks apart) if tumor burden remains $\geq 20\%$ and at least 5 mm absolute increase compared to nadir

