 - Subjects with a global deterioration of health status requiring discontinuation of treatment without radiographic confirmation of disease progression (confirmed irPD) at the time should have the reason for treatment discontinuation classified as 'clinical disease progression'. In this case, irPD cannot be assigned at the time as the overall objective tumor response. Every effort should be made to radiographically confirm irPD even after discontinuation of treatment.

Measurement and Tumor Response Assessment Based on modified irRECIST	
Measurable lesions	
 • ≥ 10 mm (unidirectional measure) • Pathologic lymph nodes: short axis ≥ 15 mm
Measurement of each lesion	The longest diameter (mm)
The sum of the measurements (SLD)	
 • The sum of the longest diameters (SLD) of all index lesions and new measurable lesions, if any • Up to 5 lesions per organ, up to 10 total
Response assessment	
 • irPD: $\geq 20\%$ increase from nadir and at least 5 mm absolute increase compared to nadir (requires confirmation) • irSD: $< 30\%$ decrease from baseline and $< 20\%$ increase from nadir • irPR: $\geq 30\%$ decrease from baseline (requires confirmation) • irCR: Disappearance of all lesions (requires confirmation)
New Lesions	The presence of new lesion(s) does not define progression. Measurable new lesions (≥ 10 mm): The measurements of the new lesions(s) are included in the SLD
Confirmation	Confirmation by 2 consecutive observations at least 4 weeks apart required for irCR, irPR and irPD.

Modified irRECIST Overall Response Assessment			
Measurable Response	Non-measurable Response		Overall Response
Index and new measurable lesions (tumor burden) ^a , %	Non-Index lesions	New non-measurable lesions	Using irRECIST
↓ 100%	Absent	Absent	irCR ^b
↓ 100%	Stable/NA	Any	irPR ^b
↓ 100%	Unequivocal progression	Any	irPR ^b
↓ $\geq 30\%$	Absent/Stable/NA	Any	irPR ^b
↓ $\geq 30\%$	Unequivocal progression	Any	irPR ^b
↓ $< 30\%$ to ↑ $< 20\%$	Absent/Stable/NA	Any	irSD
↓ $< 30\%$ to ↑ $< 20\%$	Unequivocal progression	Any	irSD
↑ $\geq 20\%$	Any	Any	irPD ^b
UE	Any	Any	UE
ND	Any	Any	UE
NA	Any	Any	UE

NA = not available; ND = not done; UE = unable to evaluate

^a Decrease assessed relative to baseline, including new measurable lesions (≥ 10 mm)

^b Response (irCR, irPR) and progression (irPD) are confirmed by a second, consecutive assessment at least 4 weeks apart.

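### Appendix D defines irPD in two conflicting ways, with and without a 5 mm absolute minimum, so progression calls can differ when the nadir is below 25 mm

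*Protocol*

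**What the plan says.** All five statements are in Protocol Appendix D.

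- **Index lesion response:** "at least a 20% increase in tumor burden compared with nadir (at any single time point"), seen on two successive assessments 4 weeks or more apart. No absolute minimum.
- **Overall response:** a rise of 20% or more "relative to nadir (minimum recorded tumor burden) and at least 5 mm absolute increase compared to nadir".
- **Response confirmation, irPD:** the burden must still be 20% or more above nadir "and at least 5 mm absolute increase compared to nadir".
- **Measurement table:** 20% or more "increase from nadir and at least 5 mm absolute increase compared to nadir (requires confirmation").
- **Table headed "Modified irRECIST Overall Response Assessment":** any rise of 20% or more is irPD. No absolute minimum; a footnote asks for a second assessment at least 4 weeks apart.

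Two further rules matter. A lesion too small to measure is recorded as 5 mm, and "If this is nadir, irPD will be judged from the tumor burden calculated using the default value". In the section on time point response assessment, irPD is ruled out before a response is assigned.

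irSD is also defined in two ways. The index-lesion and overall response text make it a residual category: neither irCR nor irPR, and no irPD. The two tables use numeric limits: less than a 30% decrease and less than a 20% increase.

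SAP Section 6 defines DOR, PFS and TTP by irRECIST progression without giving an irPD formula, and SAP Section 3.1 points to Appendix D. SAP Sections 10.6.1 and 10.6.2 use investigator-reported assessments. Protocol Section 7.4 dates progression at its first observation.

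**The concern.** Small nadirs occur in subjects with little measurable disease, including those whose tumors have shrunk most. For them a 20% rise can be a few millimetres, and the two versions of irPD then give different answers. Because Appendix D is the only source of the irPD threshold and the assessments come from about 15 sites (Protocol Section 3.2), sites could reasonably apply different versions.

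The version used decides whether a response has ended (DOR) and when progression occurred (PFS, TTP). It can also reach the primary endpoint. irPR needs two consecutive observations and irPD is ruled out first, so a small rise at the confirming scan can be read as progression instead of confirmation. In Groups 2, 4a and 4b the stage 1 recommendation turns on zero versus one response in 10 subjects. The RECIST 1.1 analysis has been dropped (SAP Section 10.10), so no second criterion would reveal a discrepancy.

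**Working it through.** The plan gives no figure to reproduce here. The check applies each version of the rule to the same measurements.

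**Inputs (Appendix D).** Relative threshold 20% over nadir; absolute threshold 5 mm over nadir; default size 5 mm; irPR at a decrease of 30% or more from baseline; irPD ruled out first.

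**Where the versions part.** For nadir N, the 20%-only version gives irPD at a burden of 1.2 × N. The two-condition version gives irPD at the larger of 1.2 × N and N + 5 mm. The two coincide when 0.20 × N = 5, so N = 5/0.20 = 25 mm. At or above 25 mm they agree; below it they can differ. With burdens in whole millimetres the largest nadir at which they differ is 20 mm (4/20 = 20%).

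**Default-value case.** N = 5 mm. The 20%-only version needs 1.2 × 5 = 6 mm. The two-condition version needs the larger of 6 and 10, which is 10 mm.

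**Three cases, irPD evaluated first:**

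| Baseline, nadir, current (mm) | Rise from nadir | Change from baseline | Index-lesion text | Overall response text | Measurement table |
|---|---|---|---|---|---|
| 10, 5, 6 | 1 mm, 20.0% | −40% | irPD | irPR | irPR |
| 20, 14, 17 | 3 mm, 21.4% | −15% | irPD | irSD | no category |
| 50, 25, 30 | 5 mm, 20.0% | −40% | irPD | irPD | irPD |

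The overall assessment table agrees with the index-lesion column in all three. In the first and third cases its rows for a 30% decrease and a 20% increase both fit, and only the order of evaluation selects irPD.

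**Confirmation.** Suppose the 6 mm reading in the first case repeats at least 4 weeks later. The index-lesion bullet and the footnote to the overall assessment table are then satisfied, and irPD is confirmed and dated at the first 6 mm scan. The separate confirmation rule is not satisfied, because the burden is 1 mm above nadir, not 5 mm.

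**Response count.** Take baseline 10 mm, first response 5 mm, next scan 6 mm. Both scans are at least 30% below baseline (50% and 40%). Under the overall response text the irPR is confirmed. Under the 20%-only version the second scan is irPD, which is ruled out first.

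**Extent on a grid.** Whole-millimetre combinations were tabulated with baseline 10 to 100 mm, nadir from 5 mm up to baseline, and current burden up to 39 mm above nadir. In 3,024 combinations the index-lesion text gives irPD and the overall response text does not: 2,747 are irPR and 277 irSD under the latter. Only those 277 have no category in the measurement table. These counts show where the rules differ; they are not expected patient frequencies.

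**Weight of one call.** At the minimum success count for Groups 2, 4a and 4b (4 of 29), one responder is 1/4 of the DOR sample. At the design response rate of 20%, 0.20 × 29 = 5.8 responders, so one is about a sixth.

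**The case against.** The best defense is that the appendix, read as a whole, favors one version. The index-lesion bullet is a component assessment. The overall response text carries the 5 mm condition twice, once in its definition and once for confirmation, and the overall assessment table comes after a measurement table that states it. That makes the two-condition version the majority reading, but it does not settle the matter: the overall assessment table is itself an overall rule, omits the condition, and has its own confirmation footnote.

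Three stronger readings are tempting and the documents do not support them.

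- *A rise of 20% or more but under 5 mm has no category.* This is true only of the measurement table, and only when the burden is also less than 30% below baseline. The overall response text makes such a rise irSD or irPR, and the index-lesion bullet makes it irPD. For example, 15 to 18.5 mm (3.5 mm, 23%) is uncategorized in the measurement table only if baseline is below 18.5/0.70 = 26.4 mm; otherwise it is irPR there.
- *A single 1 mm change establishes progression.* Every version asks for confirmation, so the rise must persist on a second scan at least 4 weeks later.
- *Every subject with a nadir below 25 mm is affected.* The versions differ only when growth is at least 20% and under 5 mm. A new measurable lesion adds at least 10 mm, so it clears the absolute minimum unless index lesions shrink at the same time.

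It is also fair that DOR, PFS and TTP are secondary and reported descriptively. That limits the consequence but does not remove it, because response confirmation bears on ORR.

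**Conclusion.** The contradiction is real and is in the current text: three of five irPD statements require 20% and 5 mm, two require only 20%, and no rule of precedence is given. Appendix D as a whole assigns conflicting categories; a true gap exists only in the measurement table, under the condition above.

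The versions can diverge for nadirs below 25 mm, with the sharpest case at the 5 mm default (6 mm against 10 mm). The effect on progression dates follows from SAP Section 6 and Protocol Section 7.4. The effect on ORR assumes that the irPD-first order is applied at the confirming scan. The documents give no distribution of nadirs or of small rises, so the number of subjects affected cannot be estimated. This should be corrected before the final analysis; it does not by itself undermine the design.

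**What to change.** For endpoint derivation:

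1. State one irPD definition in the SAP and in Appendix D: at least 20% and at least 5 mm over nadir, the version already used in three of the five places.
2. Align the index-lesion bullet and the 20% row of the overall assessment table with it.
3. Replace the numeric irSD limits in both tables with the residual definition from the overall response text. This step is needed: adding 5 mm to the 20% row alone would carry the measurement table's gap into the overall assessment table.
4. Check investigator-reported irPD against the recorded diameters for ORR, DOR, PFS and TTP, and list any call that changes.

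Confirmed irPD also governs stopping of treatment (Protocol Sections 3.1, 6.2.1.1 and 6.2.2.1). For that use the passages must be reconciled by the sponsor; no clinical rule is proposed here.

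The cost is a few lines of wording and a programming check. The SAP covers the final analysis, so the derivation rule is useful there even if enrollment has ended.

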Appendix E. Eastern Cooperative Oncology Group (ECOG) Performance Status

Grade	ECOG Performance Status
0	Fully active, able to carry on all pre-disease performance without restriction
1	Restricted in physically strenuous activity but ambulatory and able to carry out work of a light or sedentary nature, eg, light house work, office work
2	Ambulatory and capable of all self-care but unable to carry out any work activities; up and about more than 50% of waking hours
3	Capable of only limited self-care; confined to a bed or chair more than 50% of waking hours
4	Completely disabled; cannot carry on any selfcare; totally confined to bed or chair
5	Dead

Amendment 2

Protocol Title: A Phase 1b/2 Study Assessing Safety and Anti-tumor Activity of AMG 820 in Combination With Pembrolizumab in Select Advanced Solid Tumors

Amgen Protocol Number: AMG 820 20150195

Eudra CT Number: 2016-001080-36

Amendment Date: 15 June 2018

Rationale:

The following updates were made to the protocol dated 03 October 2016 to incorporate requested changes from Merck as well as clarifying language and administrative updates:

- Updated language for [Section 2.4](#) and [Section 2.5](#) with Merck-provided language for pembrolizumab product background.
- Updated language in [Section 3.4](#) to clarify that all subjects who are not DLT evaluable can be replaced.
- Updated language in [Section 3.5.1](#) to clarify the data collected for subjects who continue past 12 months and up to 24 months on treatment.
- Updated language in [Section 4](#) to clarify that all windows in Inclusion and Exclusion criteria are relative to first day of study treatment.
- Modified Exclusion Criterion to exclude subjects with history of or active pneumonitis.
- Updated relevant sections to require safety labs to be reviewed within 2 days prior to dosing.
- Updated [Table 2](#) to indicate that pembrolizumab should be permanently discontinued for Recurrent Grade 2 pneumonitis.
- Updated [Table 2](#) with footnote to indicate that treatment may possibly continue under certain circumstances of isolated elevated AST attributed to AMG 820 with agreement from Medical Monitor.
- Updated [Table 3](#) to indicate that pembrolizumab should be permanently discontinued for Recurrent Grade 2 pneumonitis or ILD.
- Provided language for corticosteroid treatment of Hepatic Toxicity ([Section 6.2.4.6](#)) or Renal Failure or Nephritis ([Section 6.2.4.7](#)): Grade 2 events should be treated with IV or oral corticosteroids while grade 3-4 events should be treated with IV corticosteroids.
- Updated the reporting period of Pembrolizumab Events of Clinical Interest ([Section 6.2.4.9](#)) to be after the first dose of pembrolizumab through 135 (+7) days after the last dose of pembrolizumab, or 135 (+7) days after initiation of a new cancer therapy.

- Updated [Section 6.2.4.10](#) through [Section 6.2.4.10.4](#) to include AMG 820 as well as pembrolizumab in diet and other considerations while taking treatment.
- Removed anticoagulation therapy from Excluded Treatments ([Section 6.9](#)) as the statement conflicted with Inclusion/Exclusion criteria.
- Provided language in relevant sections of protocol for suggested follow up frequency of AEs after EOS (Q3W for SAEs, Q2W for grade 3 or higher AEs, Q3W for other abnormalities) until return to baseline.
- Per Merck, removed all pembrolizumab PK testing from [Schedule of Assessments](#).
- As Amgen has decided to discontinue investigating the combination of AMG 820 and pembrolizumab, removed non-essential biomarker and tissue sample collection from [Schedule of Assessments](#).
- Corrected [Schedule of Assessments](#) footnotes to align with text in body of protocol.
- Removed Myeloblasts, Promyelocytes, Myelocytes, Metamyelocytes, Atypical lymphocytes from required routine hematology laboratory analytes.
- Updated [Section 9.3](#) with new template language for pregnancy and lactation reporting.
- Clarified guidance for use of PET/CT scans in [Appendix D](#) by removing vague language.
- Provided clarifying language in [Section 9.2.1](#) for when disease-related events should be considered serious adverse events.
- Corrected typo in [Section 3.5.1](#) updating the safety follow-up visit to occur 135 days after last dose of study treatment.
- Updated Sponsor Contact information.
- Updated protocol amendment date throughout document.
- Corrected grammar errors throughout document.
- Updated Page numbers in Table of Contents.

Description of Changes:

[Section: Headers](#)

Replace: 03 October 2016

With (changes are bolded): **15 June 2018**

[Section: Title Page](#)

Replace: [REDACTED] MD, [REDACTED]

With: [REDACTED] **MD MS**, [REDACTED]

[Section: Title Page](#)

Replace: [REDACTED]

With: [REDACTED]

[Section: Title Page](#)

Add: **Amendment 2 Date: 15 June 2018**

[Section: Investigator's Agreement, Paragraph 1:](#)

Replace: 03 October 2016

With: **15 June 2018**

[Section: 2.4 Non-Amgen Medicinal Product Background: Pembrolizumab:](#)

Replace entire section: In the United States, pembrolizumab is approved for patients with unresectable or metastatic melanoma and disease progression following ipilimumab and a BRAF inhibitor (if BRAF V600 mutation positive) and patients with metastatic NSCLC whose tumors express PD-L1 as determined by an FDA-approved test and who have disease progression on or after platinum-containing chemotherapy or FDA-approved therapy for EGFR or ALK genomic tumor aberrations (Keytruda® USPI, 2014).

Pembrolizumab is a humanized monoclonal antibody (IgG4 kappa immunoglobulin with an approximate molecular weight of 149 kDa) that blocks the interaction between PD-1 and its ligands, PD-L1 and PD-L2 (Keytruda® USPI, 2014). Consequently, the PD-1 pathway-mediated inhibition of the immune response is released, including the anti-tumor immune response, with resultant tumor recognition by the cytotoxic T cells.

(Hamid et al, 2013).

For additional information, refer to the Pembrolizumab Investigator's Brochure.

With:

Pembrolizumab is a potent humanized immunoglobulin G4 (IgG4) monoclonal antibody (mAb) with high specificity of binding to the programmed cell death 1 (PD-1) receptor, thus inhibiting its interaction with programmed cell death ligand 1 (PD-L1) and programmed cell death ligand 2 (PD-L2). Based on preclinical in vitro data, pembrolizumab has high affinity and potent receptor blocking activity for PD-1. Pembrolizumab has an acceptable preclinical safety profile and is in clinical development as an intravenous (IV) immunotherapy for advanced malignancies. Keytruda™ (pembrolizumab) is indicated for the treatment of patients across a number of indications. For more details on specific indications refer to the Pembrolizumab Investigator's Brochure.

[Section: 2.5 Rationale](#), Paragraph 1:

Replace: To date, anti-PD-1 antibodies have been approved for melanoma (unresectable or metastatic that progressed following ipilimumab and, if BRAF V600 mutation positive, a BRAF inhibitor), and for squamous NSCLC (metastatic disease that progressed on or after platinum-based chemotherapy). They have also shown, and are further investigated, for promising single agent activity in other selected solid and hematological malignancies. Most patients still, however, do not show a response to the monotherapy.

With: To date, anti-PD-1 antibodies have been approved for a number of indications. However, the majority of patients do not show a response to monotherapy.

[Section: 3.4 Replacement of Subjects](#):

Delete: Subjects enrolled ~~in Study Part 1~~ may be replaced if they are not evaluable for DLT (eg, a subject did not receive study treatment, or ended the study treatment before completion of DLT evaluation period for a reason other than experiencing a DLT).

~~Subjects enrolled in phase 2 who withdraw or are removed from treatment or from the study will not be replaced.~~

Section: 3.5.1 Study Duration for Subjects, Line 4:

Replace: 30

With: 135

Section: 3.5.1 Study Duration for Subjects, End of Section:

Add: **For subjects who continue treatment past 12 months and up to 24 months (if tolerable and clinical benefit is observed), only Visit Date, IP Administration, and AE/SAE information will be collected in EDC. Remaining follow-up to be performed per institutional standard of care.**

Section: 4 Subject Eligibility, End of Sentence 2:

Add: **All windows in Inclusion and Exclusion criteria below are relative to first day of study treatment.**

Section: 4.2 Exclusion Criteria, Criterion 203:

Replace:

203 Evidence of active or radiological sequelae of non-infectious pneumonitis/ interstitial lung disease.

With:

203 **Subject has history Evidence of active or radiological sequelae of interstitial lung disease, (non-infectious) pneumonitis that required steroids, or current pneumonitis. ~~Interstitial lung disease.~~**

Section: 4.2 Exclusion Criteria, Criterion 204:

Add:

204 History or evidence of other active autoimmune diseases that has required prolonged systemic treatment in past 2 years (ie, with use of disease modifying agents, ~~such as~~ corticosteroids or immunosuppressive drugs).

Section: 6.1 Classification of Product(s) and/or medical Devices(s), Line 1:

Delete: The Amgen Investigational Product **(~~except if required by local regulation~~)** use in this study is AMG 820.

Section: 6.2.1.1 Dosage, Administration, and Schedule: AMG 820, Line 6:

Replace: 48hrs

With: **2 days**

Section: 6.2.2.1 Dosage, Administration, and Schedule: Pembrolizumab, Paragraph 1, Lines 8:

Replace: 48hrs

With: **2 days**

Section: 6.2.2.2 Dosage Adjustments, Delays, Rules for Withholding or Restarting, Permanent Discontinuation: Pembrolizumab, Table 2, AST, ALT, or Increased Bilirubin Toxicity:

Add Footnote 3: **Subjects who have isolated elevated AST (with grade \leq 1 ALT and normal bilirubin) attributed to AMG 820 and are clinically asymptomatic may potentially continue with treatment upon discussion and agreement with Medical Monitor.**

Section: 6.2.2.2 Dosage Adjustments, Delays, Rules for Withholding or Restarting, Permanent Discontinuation: Pembrolizumab, Table 2, Pneumonitis Toxicity, Grade 3-4:

Add: **or Recurrent 2**

Section: 6.2.4.1 Pneumonitis and Interstitial Lung Disease (ILD), Table 3:

Add: **Recurrent Grade 2, Discontinue pembrolizumab, Supportive care per instruction for Grade 2 above.**

Section: 6.2.4.1 Pneumonitis and Interstitial Lung Disease (ILD), After Table 3:

Delete: ~~For grade 2 pneumonitis or ILD that improves to \leq grade 1 within 12 weeks, the following rules should apply:~~

- ~~• Second episodes of pneumonitis or ILD: Permanently discontinue pembrolizumab if upon rechallenge subjects develops pneumonitis \geq grade 2~~

Section: 6.2.4.6 Hepatic, Section Title:

Add: Hepatic **Toxicity**

Section: [6.2.4.6 Hepatic](#), 1st Bullet:

Replace: For grade 2 events, monitor liver function tests more frequently until returned to baseline values (consider weekly).

With: **In case of hepatotoxicity For grade 2 events**, monitor liver function tests more frequently (**see Section 6.4.2 and Appendix A**) until returned to baseline values or **stabilized and subject is asymptomatic (consider weekly)**.

Section: [6.2.4.6 Hepatic](#), 2nd Bullet:

Add: **For grade 2 events, t**Treat with IV or oral corticosteroids.

Section: [6.2.4.6 Hepatic](#), 3rd Bullet:

Add: **Subjects who have isolated elevated AST (with grade \leq 1 ALT and normal bilirubin) attributed to AMG 820 and are clinically asymptomatic may not require treatment with corticosteroids. These cases should be discussed with the medical monitor.**

Section: [6.2.4.7 Renal Failure or Nephritis](#), 1st Bullet:

Add: For grade 2 events, treat with **IV or oral** corticosteroids.

Section: [6.2.4.7 Renal Failure or Nephritis](#), 2nd Bullet:

Replace: For grade 3-4 events, treat with **IV systemic** corticosteroids.

Section: [6.2.4.9 Pembrolizumab Events of Clinical Interest](#), Line 2-3:

Replace: ...90 (+7) days after the last dose of pembrolizumab, or 30 (+7) days after initiation of a new anticancer therapy...

With: ...~~135 90~~(+7) days after the last dose of pembrolizumab, or ~~135 30~~(+7) days after initiation of a new anticancer therapy...

Section: [6.2.4.10 Diet and Other Considerations While Taking Pembrolizumab](#), Section Title:

Add: Diet and Other Considerations While Taking **AMG 820 and** Pembrolizumab

Section: [6.2.4.10.1 Diet During Treatment With Pembrolizumab](#), Section Title:

Add: Diet During Treatment With **AMG 820 and** Pembrolizumab

Section: [6.2.4.10.2 Contraception Requirements for Pembrolizumab](#), Section Title:

Add: Contraception Requirements for **AMG 820 and** Pembrolizumab

Section: 6.2.4.10.2 Contraception Requirements for Pembrolizumab, Paragraph 1,
Lines 1-2:

Add: **AMG 820 and** Pembrolizumab may have adverse effects on a fetus *in utero*.
Furthermore, it is not known if **AMG 820 or** pembrolizumab has transient adverse
effects...

Section: 6.2.4.10.2 Contraception Requirements for Pembrolizumab, Paragraph 2,
Lines 1:

Add: Subjects should be informed that taking **AMG 820 and** pembrolizumab may
involve...

Section: 6.2.4.10.3 Use of Pembrolizumab in Pregnancy, Section Title:

Add: Use of **AMG 820 and** Pembrolizumab in Pregnancy

Section: 6.2.4.10.3 Use of Pembrolizumab in Pregnancy, Line 2:

Add: ... subject will immediately be removed from the study **treatment**.

Section: 6.2.4.10.4 Use of Pembrolizumab in Nursing Women, Section Title:

Add: Use of **AMG 820 and** Pembrolizumab in Nursing Women

Section: 6.4.2 Criteria for Conditional Withholding of AMG 820 and/or Pembrolizumab
due to Potential hepatotoxicity, Paragraph 1, 4th Bullet:

Delete: OR: ALP > 8x ULN at any time>>

Section: 6.9 excluded Treatments, Medical Devices, and/or Procedures During Study
Period, 3rd Bullet, 1st Sub-Bullet:

Add:

- If the subject requires corticosteroid dosing of > 10 mg prednisone daily (or equivalent) for related toxicities, **AMG 820 and pembrolizumab** dosing must be withheld until the corticosteroid dose has decreased to ≤ 10 mg prednisone daily (or equivalent)

Section: 6.9 excluded Treatments, Medical Devices, and/or Procedures During Study
Period, 5th Bullet:

Delete: ~~anticoagulation therapy (low dose warfarin [**<2 mg/day**] or low molecular weight heparin for prophylaxis against central venous catheter thrombosis is allowed)~~

[Section: Table 5. Schedule of Assessments:](#)

Delete:

- All Whole Blood for Biomarker Analyses (Immunophenotyping)
- All Serum for Biomarker Analyses of baseline circulating markers (IL34, IL10, VEGF, MCP-1, MMPs, CSF-1)
- All Archive tumor tissue
- All New Tumor tissue for biomarker analyses
- All Anti-AMG 820 antibody collection
- All Anti-pembrolizumab antibody collection
- All Biomarker Development Blood sample
- All pembrolizumab PK testing.

[Section: Table 5. Schedule of Assessments, Footnote b:](#)

Replace: Safety follow-up will be performed approximately 135 (+7) days after the last dose of AMG 820 or the last dose of pembrolizumab, whichever is later.

With: Safety follow-up will be performed ~~approximately~~ 135 (+7) days after the last dose of AMG 820 or the last dose of pembrolizumab, whichever is later. **Suggested frequency of visits to follow any continuing events are approximately: every week for SAEs, Q2W for grade 3 or higher AEs (excluding AST elevation without drug-associated hepatotoxicity), and Q3W for other abnormalities until resolved to grade 1 or baseline.**

[Section: Table 5. Schedule of Assessments, Footnote i:](#)

Delete: ~~**Obtaining of tumor biopsies during study (week 10 +/- 2 weeks) are strongly encouraged.**~~

[Section: Table 5. Schedule of Assessments, Footnote j, Second to Last Sentence:](#)

Replace: ...prior to confirmed PD and has not had radiographic tumor imaging performed within 4 weeks (+1 week) of the visit.

With: ...prior to confirmed PD and has not had radiographic tumor imaging performed within ~~4-6~~ weeks (+1 week) of the visit.

[Section: Table 5. Schedule of Assessments, Footnote m:](#)

Replace: 48hrs

With: **2 days**

Section: [Table 5. Schedule of Assessments](#), Footnote I:

Delete:

~~PK samples indicated in table should be collected at the end of pembrolizumab infusion. AMG 820 pre-dose samples may also be assayed for pembrolizumab concentrations.~~

Section: [Table 6. Laboratory Analytes](#), Hematology:

Delete:

- ~~Myeloblasts~~
- ~~Promyelocytes~~
- ~~Myelocytes~~
- ~~Metamyelocytes~~
- ~~Atypical lymphocytes~~

Section: [7.2.2 Treatment](#), Central Laboratory Assessments:

Add: Central laboratory assessments (**refer to Schedule of Assessments as not all tests will be required after Amendment 2**):

Section: [7.2.3 Safety Follow-up Visit\(s\)](#), Central Laboratory Assessments:

Add: Central laboratory assessments (**refer to Schedule of Assessments as not all tests will be required after Amendment 2**):

Section: [7.4 Radiological Imaging Assessment](#), Paragraph 1, Line 2:

Replace: ...contrast-enhanced MRI or CT and evaluated according...

With: ...contrast-enhanced MRI ~~or~~ CT and evaluated according...

Section: [7.4 Radiological Imaging Assessment](#), Paragraph 2, Line 16:

Add: ... continue to receive treatment after **radiographic** confirmation of progressive disease...

Section: [7.6 Biomarker Development](#), During Study Treatment:

Add: Collection of at least one biopsy at the time of second CT scan (week 10 ± 2 weeks) and additional sequential tumor biopsies strongly encouraged, whenever possible, in all subjects. **Note: this biopsy will no longer be encouraged per the data of Amendment 2.**

[Section: 7.6 Biomarker Development](#), Flow Cytometry Whole Blood Samples:

Add: Refer to the Schedule of Assessments for specific time points and the laboratory manual for detailed collection and handling instructions. **Note that not all samples will be required after Amendment 2.**

[Section: 9.2.1 Reporting Procedures for Disease Related Events](#), Paragraph 2:

Delete: ~~Events assessed by the investigator to be related to the investigational medicinal product(s)/study treatment/protocol-required therapies, and determined to be serious, require reporting of the event on the Event CRF.~~

[Section: 9.2.1 Reporting Procedures for Disease Related Events](#), Paragraph 2:

Add: **Disease-Related Events assessed by the Investigator to be more severe than expected and/or related to the investigational medicinal product(s)/study treatment/protocol-required therapies, and determined to be serious, must be recorded on the Event CRF as Serious Adverse Events.**

[Section: 9.3 Pregnancy and Lactation Reporting](#), Paragraph 3:

Replace: Amgen's Global Safety will seek to follow the pregnant woman throughout her pregnancy and her baby up to 12 months after birth.

With: Amgen's Global Safety will seek to follow **with the Investigator regarding additional information that may be requested.** ~~pregnant woman throughout her pregnancy and her baby up to 12 months after birth.~~

If a female subject becomes pregnant during the study, the Investigator should attempt to obtain information regarding the birth outcome and health of the infant.

If the outcome of the pregnancy meets a criterion for immediate classification as a Serious Adverse Event (eg, female subject experiences a spontaneous abortion, stillbirth, or neonatal death or there is a fetal or neonatal congenital anomaly) the Investigator will report the event as a Serious Adverse Event.

[Section: 9.3 Pregnancy and Lactation Reporting](#), Paragraph 4+5:

Replace: If a lactation case occurs while the female subject is taking protocol-required therapies report the lactation case to Amgen as specified below.

In addition to reporting a lactation case during the study, investigators should monitor for lactation cases that occur after the last dose of protocol-required therapies through

1 week after the last dose of AMG 820 or 4 months after the last dose of pembrolizumab.

With: If a **female breastfeeds while lactation case occurs while the female subject** ~~is~~ taking protocol-required therapies report the lactation case to Amgen as specified below.

~~In addition to reporting a lactation case during the study, investigators should monitor for lactation cases that occur after the last dose of protocol-required therapies through 1 week after the last dose of AMG 820 or 4 months after the last dose of pembrolizumab.~~

[Section: 9.3 Pregnancy and Lactation Reporting](#), End of Paragraph 6:

Add: **Amgen Global Patient Safety will follow-up with the Investigator regarding additional information that may be requested.**

If a male subject's female partner becomes pregnant, the Investigator should discuss obtaining information regarding the birth outcome and health of the infant from the pregnant partner.

[Section: 9.4 Pembrolizumab Events of Clinical Interest](#), Paragraph 2, Lines 2-3:

Replace: ...90 (+7) days following cessation of pembrolizumab treatment, or 30 (+7) days after initiation of a new anti-cancer therapy...

With: ...**135 90** (+7) days following cessation of pembrolizumab treatment, or **135 30** (+7) days after initiation of a new anti-cancer therapy...

[Section: 10.3.1 Interim Analyses](#), End of Section:

Delete: ~~The study may be discontinued or modified at any time due to documented safety findings.~~

[Section: 10.3.2 Dose Level Review Team \(DLRT\)](#), End of Paragraph 1:

Add: **The study may be discontinued or modified at any time due to documented safety findings.**

[Section: Appendix D. Modified Immune-Related Response Criteria in Solid Tumors \(irRECIST\)](#), Time point response assessment using modified irRECIST, Definitions, 1st Bullet, Methods of Measurement, 3rd Sub-Bullet:

Replace: If a combined PET/CT scan is performed at the discretion of the investigator at baseline and subsequent timepoints. The CT portion of that exam should not be

substituted for the dedicated diagnostic CT exams required by this protocol. The PET portion of the CT may introduce additional data which may bias the investigator's assessment of response if it is not routinely or serially performed. However, if the investigator or the site radiologist...

With: If a combined PET/CT scan is performed at the discretion of the investigator at baseline and subsequent **timepoints, the** CT portion of that exam should not be substituted for the dedicated diagnostic CT exams required by this protocol **unless.** ~~The PET portion of the CT may introduce additional data which may bias the investigator's assessment of response if it is not routinely or serially performed. However, if the investigator~~ the Investigator or the site radiologist...

[Section: Appendix D. Modified Immune-Related Response Criteria in Solid Tumors \(irRECIST\)](#), Time point response assessment using modified irRECIST, Definitions, 2nd Bullet, Measureable disease, 4th Sub-Bullet:

Replace: New lesions: New measured lesions (ie, accurately and serially measureable in at least 1 dimension \geq 10 mm for non-nodal lesions or the short axis is \geq 15 mm for nodal lesions).

With: New lesions: New **measureable measured** lesions (ie, accurately and serially measureable in at least 1 dimension \geq 10 mm for non-nodal lesions or the short axis is \geq 15 mm for nodal lesions).

[Section: Appendix D. Modified Immune-Related Response Criteria in Solid Tumors \(irRECIST\)](#), Time point response assessment using modified irRECIST, Response confirmation, 2nd Bullet, irPD, 2nd Sub-Bullet:

Replace: In determining whether or not the tumor burden has increased or decreased per irRECIST, the local site investigator should consider all index and non-index lesions as well as any incremental new lesion(s).

